Dose level	Lenvatinib	Eribulin																	
Dose level 11	18mg/day D1-D21	1.1 mg/m  D1, D8																	
Dose level 21	14mg/day D1-D21	1.1 mg/m  D1, D8																	
Dose level 31	10mg/day D1-D21	1.1 mg/m  D1, D8																	
Dose level 12	18mg/day D1-D21	0.7 mg/m  D1, D8																	
Dose level 22	14 mg/da D1-D21	0.7 mg/m  D1, D8																	
Sample Size (according to primary endpoint)	
The study will be based on a minimax Simon 2 stage design. The ORR of interest with lenvatinib and eribulin combination is 20% (P1), and the ORR of low interest is set at 5% (P0). With an 80% power and type I error of 0.05, if no patients had an objective response to lenvatinib
																		

	and eribulin combination after the first 13 enrollments, the trial will be stopped early for futility. If at least one patient had an objective response, the study will continue to include 27 evaluable patients. With an expected 10% drop-out rate, we estimate a total of 30 patients to be enrolled in this study
Study Sites	Single nation, multi-center

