## **4 Study Design**

### **4.1 Overall plan of the study**

This is a single country multi-center, open-label phase Ib/II single-arm study in advanced adipocytic and leiomyosarcoma patients. Patients will be treated with the combination of lenvatinib and eribulin until disease progression, intolerable toxicity, or patient withdrawal.

The first 6 patients will be enrolled in a phase Ib run-in period to evaluate the safety of the combination of lenvatinib and eribulin. If more than 2 patients experience dose-limiting toxicity(s), dose adjustments will be carried out according to a pre-determined plan. If there are still more than 2 patients in the lowest pre-specified dose of combination, the combination would be declared too toxic for further treatment in STS patients.

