## 4.3 Study period and end of study

- Expected recruitment rate: 1 patient/ month
- Expected enrollment duration of the study: 24 months
- Expected follow-up period: 12 months after the last patient accrual.
- Proposed extension of study timeline to 2022/12/13 for complete recruitment, follow-up, and analysis
- Expected total patient accrual: 30 patients
- End of study:
  - This will be a 2-stage study design based on the method proposed by Simon et al. The first stage will recruit 13 patients including 6 patients in the phase Ib part. If 0 patients had any objective response, the study will be unlikely to meet the pre-determined endpoint, and thus will be terminated early. If one or more patients had objective response, a total of 30 patients could be recruited.
  - The study may also terminate early if the combination is too toxic, i.e. that there are more than 2 patients met the DLT criteria in the lowest pre-determined combination dose (detail see Figure 2) in phase Ib part.

[figure not shown]

Figure 1. The schema of the study

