#### 5.3.1 Schema for dose adjustments if more than 2 patients have DLT

The first 6 patients will be treated with lenvatinib 18 mg/day D1-D21 and eribulin 1.1 mg/m^2 D1 and D8 (Dose level 11). If no more than 2 ( $\leq 2$ ) patients had dose-limiting toxicity (DLT) in the first cycle (3 weeks), then the lenvatinib (18) and eribulin (1.1) combination will be declared safe. If more than 2 ( $> 2$ ) patients have DLT, the investigators will determine which drug is more pertinent to the DLT(s) and then will follow the customized block chart to shift the dose. If lenvatinib is determined to be related to DLT, the next lower dose would be dose level 21. Otherwise, if eribulin is determined to be the likely cause for DLT, the next dose level will be level 12. The lowest dose acceptable would be either dose level 22 or dose level 31. If still more than 2 patients have DLT in the first 6 patients of dose level 22 or level 31, the combination of lenvatinib and eribulin will be considered too toxic in STS patients.

Table 1: dose levels of lenvatinib and eribulin combination

Dose levels*	Lenvatinib	Eribulin
Dose level 11	18mg/day D1-D21	1.1 mg/m  D1, D8
Dose level 21	14mg/day D1-D21	1.1 mg/m  D1, D8
Dose level 31	10mg/day D1-D21	1.1 mg/m  D1, D8
Dose level 12	18mg/day D1-D21	0.7 mg/m  D1, D8
Dose level 22	14 mg/da D1-D21	0.7 mg/m  D1, D8

[figure not shown]

Figure 2. Schematic dose adjustment directions if more than 2 patients have DLT

The Principal Investigator will be responsible to determine the association as to which drug is more likely to be associated with the DLT and the next dose level to be started in the next step of the phase Ib (run-in) phase.

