### 5.3.3 Decision on Final Phase II dose

The final phase II dose will depend on the final result from the phase Ib part, as to which dose level did the phase Ib part confirmed to be safe (Dose 11 or 12 or 21, etc). Patients who received the same dose as to the phase II part will be included into part of the phase II efficacy analysis. (Please also refer to section 10.6 on how two institutions collaborate and determine on this issue)

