## **8 Statistical Considerations**

### **8.1 Sample size**

The study will be based on a minimax Simon 2 stage design. The ORR of interest with lenvatinib and eribulin combination is 20% (P1), and the ORR of low interest is set at 5% (P0). With an 80% power and type I error of 0.05, if no patients had an objective response to lenvatinib and eribulin combination after the first 13 enrollments, the trial will be stopped early for futility. If at least one patient had an objective response, the study will continue to include 27 evaluable patients. With an expected 10% drop-out rate, we estimate a total of 30 patients to be enrolled in this study.

If no dose de-escalation is needed in the phase Ib part, the 6 patients will be considered eligible to be included in the phase II part statistical analysis. If a lower dose is selected as the dose to go forward, only patients with the same dose as the phase II part will be included in the phase II statistical part.

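### If the run-in de-escalates, the plan does not say whether the 13 patients of the stage 1 futility look must all be at the phase II dose

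*Combined protocol and SAP*

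**What the plan says.** Section 4.3 defines stage 1 by a count that takes in the run-in without condition: "The first stage will recruit 13 patients including 6 patients in the phase Ib part". The trial ends early if none of them responds. The synopsis and section 8.1 state the same rule by enrolment order. With no responder "after the first 13 enrollments, the trial will be stopped early for futility", and otherwise "the study will continue to include 27 evaluable patients".

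The second paragraph of section 8.1 then makes use of the run-in patients conditional: "If no dose de-escalation is needed in the phase Ib part, the 6 patients will be considered eligible to be included". If a lower dose goes forward, "only patients with the same dose as the phase II part will be included in the phase II statistical part". Section 5.3.3 agrees: "Patients who received the same dose as to the phase II part will be included into part of the phase II efficacy analysis". The sample-size row of the synopsis has no such sentence.

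De-escalation is a planned branch. Section 4.1 says "If more than 2 patients experience dose-limiting toxicity(s), dose adjustments will be carried out according to a pre-determined plan", and section 5.3.1 describes a further cohort at the lowest levels: "If still more than 2 patients have DLT in the first 6 patients of dose level 22 or level 31".

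**The concern.** After one de-escalation step, the first 13 patients enrolled are 6 at the starting level and 7 at the new one. The same-dose rule excludes those 6, whereas section 4.3 counts them. Three readings are open:

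- **A.** Look after 13 enrolments and count same-dose patients only, so 7 patients.
- **B.** Look after 13 enrolments and count everyone, so 7 at the phase II dose and 6 at a dose not taken forward.
- **C.** Wait until 13 patients have been enrolled at the selected dose.

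The zero-response rule is the trial's only efficacy stopping rule. Under A, an active regimen would be stopped more often than designed. Under B, responses at another dose could decide whether the phase II dose continues. The trial is open-label and response is assessed by the investigator, so a reading chosen after responses are seen could make continuation depend on the data.

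**Working it through.** **Inputs from section 8.1:** minimax two-stage design, p0 = 0.05, p1 = 0.20, type I error 0.05 (taken as one-sided), power 0.80, stop at 0 of 13, 27 evaluable, 10% drop-out, 30 enrolled. **Inputs from section 5.3.1:** a run-in cohort of 6. A cohort of 6 at an intermediate level is assumed by analogy.

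**The plan's own figure.** An exact binomial search finds 27 as the smallest maximum size that meets both error limits. Among designs of that size, 0/13 followed by 3/27 has the smallest expected size under p0 (19.8). Success at 4 or more of 27 is not printed in the documents but follows from these inputs. Since 27/0.9 = 30, the enrolment figure also reproduces.

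With s the probability of stopping at the look and m the number of same-dose patients still to come, P(reject) = P(Bin(27,p) ≥ 4) − s × P(Bin(m,p) ≥ 4).

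- Power: s = 0.8^13 = 0.055, m = 14; 0.8177 − 0.0550 × 0.3018 = 0.801.
- Type I error: s = 0.95^13 = 0.513; 0.0437 − 0.5133 × 0.0042 = 0.042.

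**Reading A** (7 at the look, then 27 same-dose evaluable, m = 20).

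- False stop at ORR 20%: 0.8^7 = 0.210.
- Power: 0.8177 − 0.2097 × 0.5886 = 0.694.
- Type I error: 0.0437 − 0.6983 × 0.0159 = 0.033.

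**Reading B** (s = (1 − p)^7 × (1 − q)^6, where q is an assumed ORR at the other dose; final test on 27 same-dose patients).

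| q | False stop, p = 20% | Power | P(stop), p = 5% |
|---|---|---|---|
| 5% | 0.154 | 0.727 | 0.513 |
| 10% | 0.111 | 0.752 | 0.371 |
| 20% | 0.055 | 0.785 | 0.183 |

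Type I error is 0.036 to 0.042 for q from 5% to 30%. It cannot exceed P(Bin(27, 0.05) ≥ 4) = 0.044, which is the value with no look at all.

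**Reading C** returns the designed figures, provided that 27 same-dose evaluable patients follow.

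**Weight of the branch.** The documents give no expected DLT rate, so a range is assumed. With b = P(Bin(6, d) > 2), the overall false stop under A is 0.055 × (1 − b) + 0.210 × b. Overall power is 0.801 × (1 − b) + 0.694 × b.

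| Assumed DLT rate d | b | Overall false stop | Overall power |
|---|---|---|---|
| 10% | 0.016 | 0.057 | 0.799 |
| 20% | 0.099 | 0.070 | 0.791 |
| 30% | 0.256 | 0.095 | 0.774 |
| 40% | 0.456 | 0.125 | 0.752 |

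These take de-escalation to mean exactly one step. After two steps, 13 − 12 = 1 of the first 13 would be at the selected dose.

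**Accrual.** If the 30 includes excluded run-in patients, one step leaves at most 30 − 6 = 24 at the selected dose. With 10% drop-out, 24 × 0.9 = 21.6, so 21 or 22 are evaluable. With 13 same-dose patients at the look and success still at 4 or more, power is 0.63, 0.66 and 0.73 for 21, 22 and 24 evaluable.

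**The case against.** The best defence is that section 8.1 already answers the question. Its first paragraph gives the general rule and its second the exception for a lowered dose. The stage 1 look is part of the phase II statistics, so the exception can fairly be read to govern it, which gives C and 0.055. Section 4.3 is then a summary of the expected path. This stands as a reasonable reading. It does not remove the inconsistency: C departs from a look placed by enrolment order, no sentence says that the count restarts, and the synopsis lacks the exception.

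It is also true that no passage describes a 0-of-7 rule. A reader might infer from 0.210 that the plan contains such a rule, or that 0.210 is the trial's false-stop risk. The documents support neither. The figure belongs to one literal reading in one branch, and section 5.3 itself suggests that unexpected DLTs may be less likely than in a traditional phase Ib study. Nor is there an arithmetic error, since the stated design reproduces.

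Finally, the point may be moot. Version 5.0 is dated 2022-05-10 and the timeline runs to 2022/12/13, so the run-in and the look may already have passed. The documents do not state enrolment status.

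**Conclusion.** The concern holds as an inconsistency of wording confined to the de-escalation branch. Once the dose has been lowered, the unconditional stage 1 count and the same-dose rule cannot both be applied as written. At ORR 20% and after one step, the false stop is 0.210 if only the 7 same-dose patients count. It is 0.154, 0.111 or 0.055 in a mixed look for an assumed other-dose ORR of 5%, 10% or 20%, and 0.055 if the trial waits for 13 at the selected dose. Averaged over whether the branch is entered, the least favourable one-step reading gives 0.057 to 0.125 for assumed DLT rates of 10% to 40%.

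A reader might also infer an inflated type I error. That does not follow under any of the three readings as long as the final test uses same-dose patients only. What is at risk is the futility rule and power. The results rest on cohorts of 6, a single step, and the assumed other-dose ORR and DLT rates.

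**What to change.** Use the same sentence in the synopsis, section 4.3 and section 8.1: *Stage 1 is the first 13 patients enrolled at the selected phase II dose, including run-in patients treated at that dose; run-in patients at other dose levels count toward neither the 13 nor the 27.* Keeping the count in enrolled patients leaves the timing of the look unchanged when the dose is not lowered.

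In section 8.1, state whether the 30 includes excluded run-in patients. If it does, restate power after one de-escalation as about 0.63 to 0.73 (21 to 24 evaluable, success still at 4 or more).

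Cost: without de-escalation, wording only. If the run-in has already ended that way, the change merely clarifies the text. After one step, the look comes about 6 enrolments later (enrolment 19 instead of 13), roughly 6 months at the planned 1 patient per month. Then either accrual passes 30 (about 36) or the stated power is lower. If the look is still ahead, those 6 months must be set against the roughly 7 months between the version 5.0 date and the stated end of the study.

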### 5.3 Guidelines combination dose level adjustments in the phase Ib phase

The phase Ib (run-in) phase will be the first 6 patients. This is to monitor the safety of the combination of lenvatinib and eribulin in STS patients. However, this study is not the first study to use the combination of lenvatinib and eribulin in cancer patients. Thus the risk of unexpected DLT may be lower than traditional phase Ib studies. When a safe combination dose is determined, this dose would become the initial dose for the following patients. Dose adjustment for study drugs for adverse events that occur after cycle 1 should follow the protocol guidelines (section 5.4).

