## 5.4 Guidelines for dose delays and dose modifications

This part for the guideline is for all phase Ib and phase II patients..

Dose modification is made according to the greatest degree of toxicity that is graded base on Common Terminology Criteria for Adverse Events v4.03 (CTCAE). The CTCAE v4.03 can be downloaded from the CTEP home page. All appropriate treatment areas should have access to a copy of the CTCAE v4.03.

([http://ctep.cancer.gov/protocolDevelopment/electronic\\_applications/ctc.htm#ctc\\_40](http://ctep.cancer.gov/protocolDevelopment/electronic_applications/ctc.htm#ctc_40)).

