## 5.5 Duration of the treatment

- Patients may continue on study therapy until disease progression or until unacceptable toxicity occurs.
- Patients will go off study therapy if any of the following occurs:
  - The patient experiences any grade 4 toxicity after 2 dose modifications, as recommended by the protocol. If treatment is held for 2 consecutive treatment cycles due to toxicity, the patient must go off treatment.
  - The patient withdraws consent from treatment or from the study as a whole.
  - There is disease progression.
  - The treating physician feels it is necessary (e.g. due to patient non-compliance or other safety concerns)

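### Once six patients clear a dose, no rule adds later cycle 1 DLTs to the run-in count or requires a review of the starting dose

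*Combined protocol and SAP*

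**What the plan says.** Section 5.3.1 treats six patients at dose level 11 (lenvatinib 18 mg, eribulin 1.1 mg/m²) and counts DLTs in cycle 1. With 2 or fewer, "then the lenvatinib (18) and eribulin (1.1) combination will be declared safe". With more than 2, the dose moves down to level 21 or 12. Only excess DLTs at level 22 or 31 lead to the combination being judged too toxic.

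Section 5.3 then states: "When a safe combination dose is determined, this dose would become the initial dose for the following patients". Section 4.3 allows termination for toxicity if there are "more than 2 patients met the DLT criteria in the lowest pre-determined combination dose (detail see Figure 2) in phase Ib part". The other formal look, after 13 patients (4.3 and 8.1), concerns response only.

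Several safeguards apply after the run-in:
- Section 5.4, on holds and reductions, covers everyone: "This part for the guideline is for all phase Ib and phase II patients".
- Section 5.5 has off-treatment rules, among them "If treatment is held for 2 consecutive treatment cycles due to toxicity, the patient must go off treatment".
- Toxicity is graded at every visit (6.3.3), and SAEs go to the sponsor within 24 hours (9.1.2, 9.3.2).
- AEs and dose interruptions are a secondary phase II endpoint (section 2 table, 7.2.4), and 8.2.1 promises confidence intervals.
- Section 10.6 schedules a between-site meeting at least every 6 months, sooner if a site PI wishes, provided the second site has begun enrolling.

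For efficacy, run-in and later patients are pooled: "Patients who received the same dose as to the phase II part will be included into part of the phase II efficacy analysis".

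**The concern.** Six patients give little information on a DLT rate. That is true of any cohort of six and is no fault of this run-in, but it is the reason to keep counting at the same dose. Here the count ends at six, while the dose may be given to four times as many new patients.

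What section 5.4 does for one patient does not alter the dose at which the next one starts. Nor does a tally of dose reductions recover the DLT count. Grade 4 thrombocytopenia is a DLT under 5.3.2, yet 5.4.1 has both drugs held and resumed at the same level. Grade 3 hand-foot syndrome is also a DLT, and 5.4.2 permits restarting at the same dose.

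At stake is whether an accumulation of early toxicity at the phase II dose must lead to a documented decision, or does so only if someone chooses to raise it.

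**Working it through.** **Inputs from the plan.** Run-in of 6, cleared at 2 or fewer DLTs (5.3.1); total enrolment 30 (4.3, 8.1); response look at 13 (8.1). No target or maximum DLT rate is stated, so the true rates p below are assumptions, as are the pooled limits.

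**The plan's own figure.** A minimax two-stage design with response rates 5% and 20%, type I error 0.05 and power 80% gives 13 then 27 patients (stop at 0 of 13, success at 4 or more of 27), with exact error 0.0416 and power 0.8011. Then 27/0.9 = 30. The stated size reproduces and does not depend on toxicity.

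**Patients after the count.** If level 11 is kept, 30 − 6 = 24. At p = 0.40, 24 × 0.40 = 9.6 further cycle 1 DLTs would be expected.

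**Chance that a dose clears the run-in.** P(X ≤ 2) = (1−p)⁶ + 6p(1−p)⁵ + 15p²(1−p)⁴. At p = 0.40 this is 0.0467 + 0.1866 + 0.3110 = 0.544. At p = 0.50 it is (1 + 6 + 15)/64 = 0.344.

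**Precision.** The exact 95% interval for 2 of 6 is 4% to 78%. For illustration, 10 of 30 gives 17% to 53%.

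**An example pooled rule.** Pause at 6 or more of 12, 8 or more of 18, or 10 or more of 24, run-in included. These are the smallest counts for which the posterior probability of a rate above one third exceeds 0.80 under a flat prior. Start from the distribution of 0, 1 or 2 DLTs in 6, divided by P(X ≤ 2). Add six independent patients at a time, remove the paths that reach the limit, and continue. The futility stop is ignored.

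| True rate | Clears run-in | First review at 12 | at 18 | at 24 | Any review, given cleared |
|---|---|---|---|---|---|
| 20% | 0.90 | 0.005 | 0.005 | 0.003 | 1.4% |
| 25% | 0.83 | 0.015 | 0.018 | 0.014 | 5% |
| 30% | 0.74 | 0.035 | 0.047 | 0.039 | 12% |
| 1/3 | 0.68 | 0.056 | 0.076 | 0.065 | 20% |
| 40% | 0.54 | 0.117 | 0.156 | 0.128 | 40% |
| 50% | 0.34 | 0.265 | 0.289 | 0.179 | 73% |

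Under the current text, the probability of a required count-based review after the run-in is 0 in every row.

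**Sensitivity to the limits.** Limits of 5, 7 and 9 at the same looks give 61% at a true 40% and 87% at 50%, but pause 38% at one third and 6% at 20%.

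**Timing.** Section 4.3 gives "Expected follow-up period: 12 months after the last patient accrual" and "Proposed extension of study timeline to 2022/12/13 for complete recruitment, follow-up, and analysis". Taking 12 months from 2022-12-13 puts last accrual at about 2021-12-13, before version 5.0 of 2022-05-10. Actual accrual is not stated, so this is an inference.

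**The case against.** The strongest reply is that this is a design preference with much of the ground already covered. Holds, reductions, off-treatment rules and rapid SAE reporting protect later patients. Phase II already has a safety endpoint with intervals. At the expected one patient per month, a meeting every 6 months falls about every six patients, close to the looks proposed here. Section 5.3 adds that the combination has been used before, so unexpected DLTs may be fewer. The example limits miss 60% of cleared doses with a true 40% rate, the look at 12 alone catches only 12% of them, and the same PIs would decide anyway.

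Most of that stands, and it limits the point. A reader might infer that DLTs after the run-in have no consequences; sections 5.4 and 5.5 show otherwise. A reader might also take failure of the run-in to stop the trial; under 5.3.1, more than 2 of 6 at level 11 lowers the dose, so the table describes one dose level and not the fate of whole trials. Nor do the documents support calling the six-patient rule an error.

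What the reply does not supply is a trigger. The meeting depends on second-site enrolment and carries no count or dose action, the PIs' joint safety decision is specified once, after six patients, and section 5.3 quotes no DLT rate from earlier use.

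**Conclusion.** The point holds as a narrow gap: after a dose clears six patients, nothing in the plan adds later cycle 1 DLTs to the run-in count or obliges anyone to review the starting dose. If the true DLT rate were 40% to 50%, level 11 would still clear the run-in with probability 0.54 to 0.34 and could then be given to up to 24 more patients without a count-based review. These figures rest on assumed rates, independent patients and example limits. No saving in patients is claimed, because the gain is a forced pause and a written decision by the existing PIs.

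Priority lies between optional and recommended. It is lower if accrual had already ended, as the timeline suggests. It would be wrong to conclude that the response analysis is compromised: the two-stage design and its conclusion do not depend on this.

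**What to change.** **If patients remain to be enrolled.** State in 4.3 and 5.3.3 that cycle 1 DLTs, as defined in 5.3.2, are counted cumulatively at the phase II dose with the run-in included. State also that new enrolment pauses for a recorded PI decision on the starting dose at prespecified limits, for example 6 of 12, 8 of 18 or 10 of 24. The sponsor should choose the limits and give their operating characteristics in 8.1. The between-site meeting can stay as it is.

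The cost is low: AEs are already graded at every visit, so the extra work is classifying each later patient's cycle 1. At one patient per month, a 21-day cycle on average ends before the next patient is due, so counting adds no wait. The price is an occasional pause that proves unnecessary: 1.4%, 5% and 12% at true rates of 20%, 25% and 30% with these limits.

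**If enrolment is complete.** Tabulate the pooled cycle 1 DLT count at the phase II dose, with an exact 95% interval, beside the run-in count. This is a minor re-tabulation of recorded data alongside the planned AE summaries.
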